## SAP Version History

Version	Comment
Original SAP: Version 1.0 (September 2018)	same as protocol trial NA
Current SAP: Version 1.1 (October 2020, revised July 2021)	1 – Revision and re-estimation of the expected power accounting for information from the baseline period 2 – Clarification about the analysis population 3 – Specification of the core variables for multiple imputation if needed 4 – Specification of the model and covariates for the main analysis 5 – Revision and expansion of the subgroups to be evaluated

## 1. Background and rationale

Healthcare demand for critically ill patients admitted to Intensive Care Units (ICUs) has been expanding worldwide, causing a great social impact. Brazil is sensitive to this issue as it experiences great regional disparities and population ageing without adequate control of the main health determinants. This scenario justifies seeking efficient care for ICU patients.

Daily multidisciplinary round (DMR) is an approach that optimizes the ICU care. DMRs consists of systematic patient-centered discussions aiming to establish joint therapeutic goals for the next 24 hours of ICU care. However, full implementation of DMR is still challenging. Telemedicine in critically ill patients, known as tele-ICU, has gained relevance. However, the benefit of tele-ICU lacks high quality scientific evidence, particularly outside high-income countries. Furthermore, most of the studies published so far address Telemedicine in ICUs using vital signs monitoring and a continuous response system in a costly way. Thus, little is known about the use of Telemedicine focused primarily on supporting DMR, which is understood to be both effective and more feasible from the economic perspective. The TELESCOPE trial aims to evaluate whether an intervention consisting of guided DMRs, supported by a remote specialist (intensivist) through Telemedicine and audit-feedback on care performance, will reduce ICU length of stay compared to a control group.

To prevent outcome reporting bias and data-driven analysis results, the International Conference on Harmonization of Good Clinical Practice (ICH-GCP) recommends that clinical trials should be analyzed according to a pre-specified detailed Statistical Analysis Plan (SAP). This document presents the updated and finalized SAP of TELESCOPE trial. Recruitment for

the trial has now been completed, but data collection is still running and no data analysis has yet been undertaken.

## 2. METHODS

### 2.1. Study design and setting

The TELESCOPE trial is a national, multi-center, controlled, open label, cluster-randomized trial. The study tests the effectiveness of daily multidisciplinary rounds conducted by an intensivist through Telemedicine in Brazilian ICUs. The protocol was approved by local Research Ethics Committee (IRB) of the coordinating study center (Hospital Israelita Albert Einstein) (CAAE: 01523118.0.1001.0071) and by the local IRB from each one of the 30 ICUs, following the Brazilian legislation.

### 2.2. Inclusion and exclusion criteria

#### 2.2.1. Eligibility criteria for ICUs (clusters)

At the cluster level, ICUs of public or philanthropic hospitals, with a minimum of 8 ICU beds and with on-site registered doctors and nurses were eligible for inclusion.

We excluded ICUs that already presented DMRs, defined as:

1) Meetings (DMRs)  $\geq$  3 times per week, during weekdays, conducted by a certified intensivist and documented in medical records with fixed visit length (>5 min / patient), using some supporting tool (checklist or standard form), goal-oriented, based on established protocols, including all the patients admitted to the ICU

or

2) Monthly management of indicators (audit and feedback) with specific planning. We also excluded specialized ICUs (ICUs admitting exclusively cardiac surgery, neurological, burned patients) and step-down units or coronary units. Only one unit per hospital was allowed.

#### 2.2.2. Inclusion criteria for patients

At the patient level, all consecutive patients admitted to the ICU, aged 18 years or older after the beginning of the trial.

#### 2.2.3. Exclusion criteria for patients

We excluded patients admitted to the ICU due to justice-related issues (since in such circumstances the ICU admission or discharge may be determined by the law rather than by medical reasons) and patients previously included in the TELESCOPE trial (for the analysis of the primary outcome).

### 2.3. Intervention

Briefly, the trial intervention consists of DMR led by remote intensivists with the local multidisciplinary team (doctor, nurse and physiotherapist). DMRs take place from Monday to Friday, in predetermined hours (mostly during the mornings), using Telemedicine equipment, and they approach every patient admitted to the participating ICUs. Clinical protocols in texts and video formats (developed and used during the tele-intensivists training period) were made available to physicians and multidisciplinary team of the ICUs in

the intervention arm, right after randomization and establishment of a DMR routine. Tele-intensivists do not write medical prescriptions, nor do they give direct orders to the local care team for procedures or interventions. DMRs may be postponed, interrupted or suspended in case of urgency / medical emergency situations that may hinder participation of local doctors.

Additionally, ICU performance indicators are presented for each coordinator of the participating ICUs as well as for tele-intensivists, and monthly remote meetings between the local ICU team and the respective tele-intensivist are organized to discuss these indicators and to establish possible improvement action plans.

Control Group (usual care): no interventions are delivered to the ICUs randomized to the control group, except for the systematic data collection required for the comparisons described in the trial objectives. However, unlike in the ICUs of the intervention group, the ICU performance indicators originated from the collected data are not discussed with the care team or the coordination of the participating ICUs.

## 2.4. Randomization and masking

After a 2-month observation period (baseline period) in which performance indicators for eligible ICUs were collected without any intervention (with the purpose of obtaining data for randomization, analysis and characterization of the initial ICU status), the ICUs eligible for the study were randomized. The 30 ICUs were randomly assigned to either the intervention group (n=15) or the control group (n=15) using a restricted randomization algorithm that minimizes imbalance between treatment groups across the following baseline covariates at the ICU level:

- 1) number of ICU beds

- 2) mean SAPS 3, in points
- 3) mean ICU length of stay (LOS), in days
- 4) Standardized mortality rate (SMR)
- 5) Standardized resource use (SRU), and
- 6) A two-category dummy indicator for Brazilian region where the ICU is located (regions South and Southeast x regions North/Northeast/Central-West).

We followed all the steps recommended by Carter and Hood during the application of the minimization algorithm. The randomization was performed at three times, including 14 units during the first randomization, followed by 7 and 9 units (Figure 1). We decided a priori to randomize at three times and the number of units at each randomization was pragmatic, allowing for ethical approval and completion of the baseline period, respecting the minimum of eight units during first randomization and minimum of six on subsequent randomizations.

For the first randomization, we followed the steps: 1) the database with the baseline data (2 months) were locked, 2) derivation of the six covariates per unit, 3) run the algorithm, generating the potential combinations of unit's allocation, 4) a random combination of allocations was selected. The order of each unit in the database was randomly sorted before the algorithm, as well as the order of potential allocations. The select allocation was coded as 0 and 1 by the algorithm. To select whether intervention would be 0 or 1, we performed the final simple randomization and 0 was allocated to the intervention arm. For the second and third blocks, we followed the same steps: we entered the baseline data of the previous block with its allocation and the new covariates. The algorithm accounts for the previous block covariates to calculate the new balance between

arms. We applied the same random sorting of order and potential unit allocations. The meaning of 0 and 1 was kept the same as the first block randomization (i.e., 0 to intervention and 1 to control) because it must follow the first block ascertainment. To ensure allocation concealment, all units were enrolled prior to randomization and the Ethics approval and the ICU and hospital coordinators signed the agreement with commitment to the trial; the statistician responsible for the randomization list received only the ICU identifier code, unaware of which unit it referred to; the allocation list was sent to the study coordinator, who informed simultaneously the ICUs about the randomization and allocation.

The allocations were done after the completion of the baseline, on 05 August 2019, 16 October 2019, and 29 January 2020, using the software R (v. 3.5.2).

**Figure 1. Time periods of 30 units in the TELESCOPE trial.**

Randomization	Number of Units	2019								2020				...	2021
		Jun	Jul	Aug	Sept	Oct	Nov	Dec	Jan	Fev	Mar	...	April		
First	14	Baseline	Baseline	Intervention / Control	End enrollment*										
Second	2	Waiting IRB	Baseline	Baseline	Interstitial	Intervention / Control	End enrollment*								
	5	Waiting IRB	Waiting IRB	Baseline	Baseline	Intervention / Control	End enrollment*								
Third	2	Waiting IRB	Waiting IRB	Waiting IRB	Baseline	Baseline	Interstitial	Interstitial	Intervention / Control	End enrollment*					
	4	Waiting IRB	Waiting IRB	Waiting IRB	Waiting IRB	Baseline	Baseline	Interstitial	Intervention / Control	End enrollment*					
	3	Waiting IRB	Waiting IRB	Waiting IRB	Waiting IRB	Waiting IRB	Baseline	Baseline	Intervention / Control	End enrollment*					

\* From April the data collection will continue until hospital outcome or 90-days post ICU admission. The intervention will be maintained in the whole unit until the last included patient is discharged from the ICU.

Interstitial was the period when the ICUs completed their baseline period of two months and were waiting for more blocks to complete their 2-month period to be randomized as a block.

The intervention is open due to the nature of the study (Tele-ICU rounds, quality improvement meetings and delivery of evidence-based clinical protocols). The steering and scientific committees are blinded to the DMRs and monthly feedback/audit meetings.

## 2.5. Outcomes

### 2.5.1. Primary outcome

At an individual level, the primary outcome of this trial is ICU length of stay, measured in days, taking into account the time interval in hours between patients' ICU admission and ICU discharge times (i.e., transfer to another care facility or another hospital) or ICU death, as defined by the hospital's system date and time. Date and time will be entered by the health care worker responsible for data collection. ICU LOS will be derived in 24h periods with decimal places, as recommended.

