### 2.5.2. Secondary exploratory outcomes

The secondary outcomes of this study include assessing the impact of interventions implemented through Telemedicine compared with a control group in the following outcomes:

At the unit level:

- Classification of the unit according to the profiles defined by the SRU and the SMR. The SRU reflects the observed / expected rate of resources used (estimated as ICU length of stay for surviving patients), adjusted by the patient's severity of illness (SAPS 3).

The SMR reflects the observed / expected rate (according to severity score) of hospital deaths. The profiles are a combination of SMR (above or below median) and SRU (above or below median): Each unit can be assigned to one of the four groups:

"most efficient" (SMR and SRU < median); "least efficient" (SMR, SRU > median);

"overachieving" (low SMR, high SRU), "underachieving" (high SMR, low SRU).

At an individual level:

- In-hospital mortality, defined as death by any cause, within the period from the date of ICU admission to the date of hospital discharge or death, whichever comes first.
- Incidence of central line-associated bloodstream infection (CLABSI), as defined by the CDC.
- Incidence of ventilator-associated event (VAE), as defined by the CDC.
- Incidence of catheter-associated urinary tract infection (CAUTI), as defined by the CDC.
- Ventilator-free days at 28 days, defined as the number of days from successfully weaning to day 28; patients who died before weaning were deemed to have no ventilator-free days
- Rate of patients receiving oral or enteral feeding, defined as any amount of oral or enteral diet, during ICU stay
- Rate of patients under light sedation or alert and calm [Richmond Agitation-Sedation Scale (RASS) = -3 to +1]
- Rate of patients under normoxemia [peripheral oxygen saturation (SpO2) between 92% and 96%]

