### 3. Data collection and management

A detailed description of data collection and management is described in the protocol paper. Data collection procedures will be identical in the ICUs assigned to control and to intervention arms, following 1) At ICU admission, including date and hour of admission,

demographic variables, SAPS 3 and SOFA score, reason for admission, comorbidities, functional status, organ support, among others; 2) Data regarding data to ascertain secondary and tertiary outcomes will be collected daily, including documented treatment goals from the DMR; 3) Upon ICU discharge, data on date and time of ICU discharge, place of discharge, and outcome; 4) And finally, at hospital discharge, date and time and outcome.

Trained health care workers collected data, without any involvement of the study committees and investigators. We developed standard CRFs for the trial, with extensive validation and piloting aiming to achieve clarity and consistency. Data was imputed using electronic CRFs in the Research Electronic Data Capture system (REDCap®, USA) via Internet and hosted on a server at the Hospital Israelita Albert Einstein/São Paulo - Brazil.

Data from the intervention arm regarding adherence to the intervention was collected. The main indicators for adherence to the intervention were defined as:

- a. DMR rate per site/bed/day and DMR duration (including individual and periodic feedback to each tele-intensivist).
- b. Rate of recommendations made and validated (accepted and not accepted)/DMR.
- c. Monthly meeting on performance indicators reports: tele-intensivists will send monthly reports to study team, including the executive summary (file sent to the leaderships of each study center/intervention arm, before the monthly meeting) and the meeting record file (structured data about highlighted indicators, action plan, responsibility, and due dates).
- d. Access to the clinical protocols: absolute number of accesses to the video-protocols will be provided and followed.

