#### 4.1.5. Other issues

We will not compare baseline characteristics between treatment groups with Null hypothesis significance testing (NHST).

We will evaluate the calibration for in-hospital mortality of the SAPS3 score with data from the baseline period. If necessary, we will recalibrate the model for the studied population. All analyses will be performed with program R (3.4.1 version, the version will be updated at the time of analysis).

The TELESCOPE trial has been running during the COVID-19 pandemic. It is likely that the pandemic changed the usual characteristics of the admitted patients, both if an ICU from the TELESCOPE trial becomes a reference for COVID-19 patients or for non-COVID-19 patients. The ICU performance, both at control and intervention arms, could have influenced the decision-makers at the Federal, State and Municipal level to decide on referring an ICU to be COVID-19 or not. As ICU performance is, in this case, post-randomization, we will not adjust for whether an ICU is reference for COVID-19 or not in the analysis, otherwise it will break the randomization. Neither the steering committee nor tele-intensivists were responsible for any decision about an ICU being a reference or not to COVID-19.

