##### *4.2.3.1. Readiness for discharge*

The primary outcome – ICU LOS – is an outcome that depends also on factors outside the ICU for those that improved during the ICU stay, such as ward bed availability. For this reason, we specified to also measure the ICU LOS in terms of readiness for discharge, i.e., days from ICU admission to the first day the attending team defined the patient was ready to be discharged alive. This variable was measured during the daily collection data and will be measured as counts, because we will not have time accuracy for its measurement. The attending clinicians were not aware that this would be an outcome of the TELESCOPE trial. We will fit the Equation (1) using generalized linear mixed models to accommodate it using a Poisson or negative-binomial family with a log link.

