##### *4.2.3.2. Competing risk of death*

The primary outcome – ICU LOS – is subject to the competing risk of death. Therefore, the ICU LOS represents a composite summary of two process: time to ICU discharge alive and time to ICU death. There are alternatives to deal with this scenario, such as 1) fitting competing risk models, modeling time to discharge alive and consider time to ICU death as a competing event, 2) analyzing LOS separately between ICU survivors and

non-survivors, 3) weighting differently the LOS for those who died, among others. As expected, the potential different results on the primary outcome analysis will likely occur or be relevant only if the intervention has an effect on mortality. We consider this a secondary analysis because, *a priori*, we did not expect a major impact of the intervention on mortality. In this sensitivity analysis, we will use the competing risk framework, presenting the analysis with cause-specific hazard ratios and sub-distribution hazard ratios for the time to discharge alive. The models will be adjusted for the same six covariates as the primary analysis, and the baseline period will be accounted as the mean ICU LOS at the unit level in the baseline period. We will account for the correlated data structure with a “shared frailty model”.

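### A live transfer to another hospital ends the primary ICU stay and falls under discharge alive in the competing-risk analysis, with no separate coding of transfers

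*SAP*

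**What the plan says.** - **Primary outcome (SAP 2.5.1).** ICU length of stay runs from admission to "ICU discharge times (i.e., transfer to another care facility or another hospital) or ICU death". A transfer to another hospital is therefore a completed stay, whatever the patient's condition on leaving.
- **Competing-risk sensitivity analysis (4.2.3.2).** The rationale is that "the ICU LOS represents a composite summary of two process: time to ICU discharge alive and time to ICU death". The approach is described as "modeling time to discharge alive and consider time to ICU death as a competing event", and the results are to be "cause-specific hazard ratios and sub-distribution hazard ratios for the time to discharge alive". No category, censoring rule or exclusion is given for transfers.
- **Readiness-for-discharge sensitivity analysis (4.2.3.1).** The outcome is "days from ICU admission to the first day the attending team defined the patient was ready to be discharged alive". It is motivated by ward-bed availability. No value is stated for a patient who leaves before that day.
- **Data (3).** At ICU discharge the trial collects "data on date and time of ICU discharge, place of discharge, and outcome". No stated analysis uses the place of discharge, and the table shells in 5.1.3 and 5.1.4 do not show it.

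**The concern.** Section 4.2.3.2 exists because LOS mixes ways of leaving the ICU that mean different things. It separates death from the rest but leaves one further mixture in place. A patient who has recovered and a patient sent on to another ICU are the same event. Because 2.5.1 names transfer as an end of stay and 4.2.3.2 offers only two exits, a live transfer must fall under discharge alive.

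Suppose that, after randomisation, one arm transfers out more patients who are still critical. Its mean LOS falls and its discharge-alive hazard rises, without any faster recovery. The competing-risk analysis would then move with the primary result instead of exposing the reason for it. What is at stake is how a positive LOS finding is read: as earlier recovery, or partly as stays that continued elsewhere.

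**Working it through.** **Inputs from the SAP.** Target 8.0 to 6.5 days, SD 10, ICC 0.018, 15 ICUs per arm, 500 patients per ICU, CV of cluster size 0.15, power 80%, alpha 5% (2.6.1; two-sided assumed). Baseline mean LOS 7.8 days (2.6.2). LOS is log-transformed (4.2.1). The SAP gives no transfer rate, so the arm difference q is an assumption and is varied.

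**Step 1: the plan's own figure.** Design effect = 1 + ((1 + 0.15²) × 500 − 1) × 0.018 = 10.18. Standard error = 10 × √(2 × 10.18 / 7500) = 0.521 days. With a non-central t on 28 df, a 1.5-day difference has 79.3% power (82.1% by the normal approximation). The stated 80% reproduces, so 1.5 days is a fair yardstick.

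**Step 2: the target on the log scale.** ln(6.5/8.0) = −0.208. This treats the target as a ratio and assumes the same log-scale spread in both arms.

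**Step 3: effect of one transfer.** Let a transfer fall at a uniformly random fraction U of the stay the patient would otherwise have had.
- Log scale: E[ln U] = −1, so an excess q shifts mean log LOS by −q.
- Days: half the stay is lost on average, 7.8/2 = 3.9 days, so an excess q shifts mean LOS by −3.9q.

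**Step 4: size with no true effect on recovery.**

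| Arm difference q | Log-scale shift | Share of 0.208 | Shift in days | Share of 1.5 days |
|---|---|---|---|---|
| 3 points | −0.03 | 14% | −0.12 | 8% |
| 5 points | −0.05 | 24% | −0.20 | 13% |
| 10 points | −0.10 | 48% | −0.39 | 26% |

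Mimicking the whole target would take 0.208/1 = 21 points on the log scale, or 1.5/3.9 = 38 points in days.

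**Step 5: sensitivity to when the transfer happens.** Cut each transferred stay to a fixed fraction f of its full length (mean 8 days). The shift is q × 8 × (1 − f) in days and q × ln f on the log scale. For f from 0.5 down to 0.1:
- q = 2 points: 5–10% of the target in days, 7–22% on the log scale.
- q = 5 points: 13–24% in days, 17–55% on the log scale.
- q = 10 points: 27–48% in days, 33–111% on the log scale.

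The log scale is the more sensitive because very short stays weigh heavily there. The top figure needs a 10-point excess with every transferred stay cut to a tenth.

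**Step 6: the competing-risk analysis.** This was simulated with lognormal LOS (mean 8, SD 10), an assumed ICU mortality of 25%, and transfers coded as discharge alive. The fraction f was 0.25 or 0.5 and q was 2 to 10 points. The ratio of crude discharge-alive rates, standing in for the cause-specific hazard ratio, was about 1.02–1.12. An approximate sub-distribution hazard ratio at 30 days was about 1.02–1.08. Both favour the arm with more transfers, as the LOS result does.

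**The case against.** The best defence has several parts.

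- **The primary definition is not an error.** Ending an ICU stay when the patient leaves that ICU is a legitimate convention, and it contradicts nothing in the SAP. This stands, and the definition should be kept.
- **One planned analysis already bears on the matter.** A reader might infer that nothing in the SAP separates leaving from being ready to leave. That goes too far, because 4.2.3.1 does so in part. But it was written for delayed exit and is silent on a patient who leaves unready, so that patient's value would have to be chosen at analysis.
- **Bias needs an arm difference.** Transfers that are equally common in both arms do not bias the comparison. A stable difference between ICUs is partly absorbed by the baseline data in Equation (1). Movement that varies between ICUs without following arm enters the cluster-by-period term as noise. This stands.
- **The COVID-19 text is not evidence of differential transfer.** Section 4.1.5 says the mix of admitted patients may change, "both if an ICU from the TELESCOPE trial becomes a reference for COVID-19 patients or for non-COVID-19 patients". A reader might infer that such designations emptied units in one arm and produced a much larger artefact. The section does not mention transfers, and it says that neither the steering committee nor the tele-intensivists decided reference status. The SAP's own figures also limit the size. Over 18 months (about 548 days) the average census is 500 × 7.8 / 548, or about 7 patients, which is 1.4% of an ICU's 500. The mean remaining stay of patients present on a given day is (9.8² + 7.8²)/(2 × 7.8) = 10.06 days. Emptying every ICU in one arm once, and none in the other, would give about 0.014 × 10.06 = 0.14 days, roughly 10% of the target. A 10-point difference would take about seven such evacuations.
- **In-hospital mortality.** Section 2.5.2 counts deaths "within the period from the date of ICU admission to the date of hospital discharge or death". A reader might infer that a transferred patient is scored as a survivor. The SAP gives no transfer rule there, follows patients to hospital outcome or 90 days (Figure 1), and leaves data-collection detail to the protocol paper. The inference is possible but not established.

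**Conclusion.** The gap is real and modest. As written, a still-critical patient transferred out alive has a completed stay in the primary analysis and counts as discharged alive in 4.2.3.2. Readiness for discharge guards against this only in part. If such transfers differ between arms after randomisation, LOS and the discharge-alive hazard ratios err in the same direction.

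Under uniform timing, a difference of 3, 5 or 10 points mimics about 14%, 24% or 48% of the target on the planned log scale, and 8%, 13% or 26% in days. This rests on an assumed arm difference, since the SAP gives none, and on transfers falling at random with respect to the length of stay. A full false effect would need a large imbalance. The documents do not show that an imbalance exists. They show that, if it did, the planned competing-risk analysis could not reveal it.

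**What to change.** - Keep the primary LOS definition.
- In 4.2.3.2, use place of discharge to code transfer to another hospital or another ICU as a separate competing event, not as discharge alive. Report the cause-specific hazard ratio for transfer alongside those for discharge alive.
- Tabulate transfers by arm and period beside the LOS result in 5.1.4.
- In 4.2.3.1, state how readiness is scored for a patient who leaves before being judged ready.

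A separate analysis censoring stays at transfer is not needed. For the cause-specific hazard of discharge alive it is identical to the competing-event coding, and the linear mixed model on log LOS cannot take censored values. Nor need the LOS conclusion be made conditional on agreement between analyses.

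The cost is SAP wording and a small amount of analysis, with slightly fewer discharge-alive events in the sensitivity model. No new data are needed, provided the recorded place of discharge distinguishes another hospital or ICU from other destinations; the SAP does not list its categories. Section 1 states that no analysis has yet been done, so the rule can still be fixed before results are seen.
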